- The patients will be randomized into the traditional vs. oral treatment groups (see below for details and protocol). The protocol for each group will be placed in sealed envelopes, 65 for each group, and picked randomly for each patient.
- The patients will attend their normal preoperative visits with the surgical team as well as their regularly scheduled preoperative clearance visit with the medical doctor (Surgery Welcome Center)
- Standard preoperative labs will be obtained (hematocrit, basic metabolic panel), at their preoperative appointment
- Additional preoperative labs will include urine specific gravity to monitor patient hydration which will be obtained the morning of surgery; this will be paid for by the CJR research fund.
- Standard laboratory values (hematocrit and basic metabolic panel) will be obtained postoperative day #1 and #2, if the patient has not been discharged.
- Urine output will be monitored on postoperative day #1 and #2 which is standard protocol
- Additional test will include urine specific gravity on postoperative day #1 and #2 as a marker of hydration as long as the patient is still in the hospital. If the patient is discharged postoperative day #1 we will collect this once in the morning, and once more before they are discharged. Payment of the cost of these laboratory evaluations will come from CJR research funds.
- Patients are encouraged to attend physical therapy 2-3 times a week for 6 weeks. Physical therapy log is attached with ROM and Girth measurement collected once a week for 4 weeks.
- Hematocrit, basic metabolic panel and urine specific gravity 2 weeks postoperatively at their routine follow-up visit will also be obtained. The cost of these laboratory tests will come from CJR research funding.
- Sixty-five patients in each group will be recruited for this study (see stats for power analysis). We will increase our number of enrollment to 75 in each group to account for patients that drop out and withdrawals from the study.

Traditional Fluid Protocol

- NPO Clears and Food after midnight.
- 2 Liters of lactated ringers administered by anesthesia intraoperatively.
- Postoperatively - 2 Liters of Crystalloid while in PACU and Inpatient Room for a Total of 4 Liters of Crystalloid within 24 hours.
 - Patient will receive 500 milliliters while in PACU and 1500 milliliters while in their Inpatient Room, for a total of 2 Liters.

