F. Thromboembolic Disease: Screening will be based on clinical assessment of the participating medical team members, which is standard protocol with all of our patients. The incidence of thromboembolic events will be recorded. All patients in the study will use aspirin 81 mg twice daily for DVT prophylaxis.

G. Muscle Strength: quadriceps strength will be assessed on POD #1 and 2 by research staff (in the hospital) and repeated at 2 and 6 weeks postoperatively at their standard of care follow-ups in the office by research staff. The strength testing will be calculated using a handheld dynamometer which is standard testing for strength in many post-operative patients currently.

H. Functional Performance Assessment: Functional tests will be performed at their preoperative appointment and once again at their 2 and 6 weeks postoperatively and will include the timed up and go (TUG) and the 30 second sit-to-stand tests. The tests will be performed in the office by research staff. These are standard tests that are often performed in physical therapy clinics to assess patient progress.

I. Length of the Hospitalization & Readmission Incidence will be recorded for both groups.

J. Postoperative Pain Assessment: Pain will be assessed using a pain VAS scale daily while hospitalized, then three times per day for 4 weeks postoperatively. Patients will be given a log to record these measurements outside of the hospital setting.

K. Adverse Events: episodes such as symptomatic hypotension (light-headedness, syncope), emesis, the need the IV fluid boluses, and other hospital and post-discharge events will be recorded.

L. Blood Pressure: this will be recorded in the Preoperative Care Unit, PACU, upon arrival to the nursing unit, and every 8 hours thereafter while hospitalized. This is standard practice for all of our patients currently.

M. PONV (Post-operative Nausea and Vomiting) - PONV will be assessed throughout their hospital stay; vital signs are checked per hospital nursing protocol, patients will be asked about Nausea: None, Mild, Moderate or Severe.

N. Patient Reported Outcome – We will be collecting the Knee Society Score(KSS) Knee injury and Osteoarthritis Outcome Score (KOOS) and the VR-12 from the patients pre-operatively as well as at their 2 week and 6 week follow up appointments. These are validated patient reported outcome measures that are already collected as standard of care at Colorado Joint Replacement.

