O. Pressors – We will be collection the total amount of any pressor drugs (e.g. Ephedrine and Phenylephrine) given intra-operatively and in PACU in both groups.

P. Oral Fluid Intake Log – The patients that are in the Oral group will have an additional page to keep track of their fluid intake prior to surgery.

Q. Bioimpedance machine - This will be used to track patients body composition before and after surgery. Research staff in the office will collect this information at the patient's pre-op visit, POD#1 and 2 as well as their 2 week and 6 week visit.

R. Body Temp – The patient's body temp will be recorded pre-operatively as well as in the recovery room.

S. Time from their last clear fluid drink to the start of anesthesia, this start up time will be recorded for both groups.

T. Patient perception/satisfaction with their fluid protocol.

Patient Withdrawal: subjects may withdraw from the study for any reason at any time. Should a subject decide to withdraw from the study, all data collected up to that point will be deleted and not used for statistical analysis. Withdrawal from the study will not affect the patient's treatment after their total knee arthroplasty.

3. Scientific Background of the Study – As stated in the “purpose” section –

Evidence-based guidelines on optimal perioperative fluid management have not been established in patients undergoing orthopaedic surgery. Recent randomized trials in major abdominal surgery suggest that large amounts of fluid may increase morbidity and hospital stay. This study will investigate the effects of two regimens of intraoperative fluid management (“traditional” vs. “oral”) with physiologic and patient function as primary outcome measures after surgery.

4. Specific Aims of the Study – This study will investigate the effects of two regimens of intraoperative fluid management (“traditional” vs. “oral”) with physiologic and patient function as primary outcome measures after surgery.

5. Description of risks and measures to minimize risks.

- All patients, regardless of their volume protocol (traditional vs. oral), will follow a traditional post-operative course which includes daily labs and monitoring physiologic status from both the orthopaedic and general medicine team.
- All patients will have traditional post-operative follow-up care which will not be varied.

Surgical Risks:

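### Deleting all data from any patient who withdraws removes randomised patients, completed outcomes and recorded adverse events from the comparison

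*Combined protocol and SAP*

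**What the plan says.** All references are to the combined protocol and SAP.

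- **Section 2, Patient Withdrawal.** "subjects may withdraw from the study for any reason at any time". On withdrawal, "all data collected up to that point will be deleted and not used for statistical analysis". No exception is made for finished outcomes, baseline values or adverse events.
- **Section 2, Procedures.** "The patients will be randomized into the traditional vs. oral treatment groups". This step is listed before the preoperative visits and surgery. Enrolment is raised from 65 to 75 per group "to account for patients that drop out and withdrawals from the study", so withdrawals are expected.
- **Section 2, Primary Outcomes.** Several items are complete within hours or days. Pressor drugs (O) are totalled as "given intra-operatively and in PACU in both groups". For item R, "body temp will be recorded pre-operatively as well as in the recovery room". For time since the last clear drink (S), "this start up time will be recorded for both groups". For nausea and vomiting (M), "PONV will be assessed throughout their hospital stay". Item L is in-hospital blood pressure. Adverse events are item K and include light-headedness, syncope, emesis and the need for fluid boluses.
- **Section 5.** The data safety monitoring plan lists adverse event and serious adverse event reporting, and an independent physician reviews events quarterly. The text available does not say whether a withdrawn patient's events are retained.
- **Section 9, Methods of Evaluation.** Post-treatment outcomes are compared, for example by t-test, with baseline equivalence checks. No analysis set or missing-data method is given that would override the deletion rule.

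**The concern.** Randomisation makes the arms comparable as they were formed. Removing patients because of a later decision of their own gives that up. For an outcome measured before the patient withdrew, nothing is missing and a full as-randomised comparison is available, yet the rule forgoes it.

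If withdrawal is related to outcome differently in the two arms, the remaining comparison is biased. The regimens ask different things of patients (oral loading with an intake log, against overnight fasting and intravenous fluid), so this cannot be ruled out. A patient who faints or vomits and then withdraws disappears from the adverse-event comparison. With baseline values deleted as well, leavers cannot be compared with stayers, and the section 9 balance checks no longer cover everyone randomised.

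The rule has limits:

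- It applies to patients who withdraw, not to those merely lost to follow-up.
- Those who leave before surgery lose only baseline and other preoperative data.
- Outcomes due after withdrawal, such as the 2- and 6-week functional tests and KOOS, are missing with or without deletion.

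**Working it through.** **The plan's own figures.** Bonferroni: 0.05/8 = 0.00625, as stated. For effect size 0.6, power 0.8 and α = 0.00625, a t-test needs 64 per group one-sided and 73 two-sided. The stated figure of about 65 therefore reproduces only one-sided, and sidedness is not given. The allowance is 75 − 65 = 10 per group, or 10/75 = 13.3%. It is a planning margin, neither a stated rate nor a cap.

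**Assumptions below.** Withdrawal counts k, the correlation r between withdrawal and outcome, event rates and relative chances of leaving are all assumed. The bias results apply only to outcomes complete before withdrawal.

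**Continuous outcome, no true difference, k of 75 leaving one arm.** Let f = k/75 and z = Φ⁻¹(1 − f).

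- Distance of leavers from their arm's mean = r·φ(z)/f
- Shift in the mean of those remaining = r·φ(z)/(1 − f)
- Type I error from the noncentral t, arms 75 − k and 75, noncentrality = shift/√(1/(75 − k) + 1/75)

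For k = 10 and r = 0.5: f = 0.1333, z = 1.111, φ(z) = 0.2153. Leavers lie 0.5 × 0.2153/0.1333 = 0.807 SD from the mean. The shift is 0.5 × 0.2153/0.8667 = 0.124 SD. Noncentrality is 0.124/√(1/65 + 1/75) = 0.733, and the error at nominal 0.05 is 0.1125.

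| k (one arm, r = 0.5) | Leavers (SD) | Shift (SD) | Error, nominal 0.05 | Error, nominal 0.00625 | Simulated at 0.05: deleted / kept |
|---|---|---|---|---|---|
| 2 | 1.157 | 0.032 | 0.0542 | 0.0072 | 0.0544 / 0.0486 |
| 5 | 0.970 | 0.069 | 0.0699 | 0.0109 | 0.0710 / 0.0491 |
| 10 | 0.807 | 0.124 | 0.1125 | 0.0224 | 0.1144 / 0.0495 |

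The simulation used 100,000 trials per row. Sensitivity at nominal 0.05 for k = 2, 5, 10:

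- r = 0.3: 0.0515, 0.0571, 0.0721
- r = 0.7: 0.0583, 0.0893, 0.1748
- Same pattern in both arms, r = 0.5 (simulated): 0.0536, 0.0549, 0.0575
- Withdrawal unrelated to outcome, k = 10 in one arm (simulated): 0.0495

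**Adverse events.** Take an arm with 15 of 75 events (20.0%) and 10 withdrawals. If 0, 2, 5 or 10 of the leavers had an event, the reported rate is 15/65 = 23.1%, 13/65 = 20.0%, 10/65 = 15.4% or 5/65 = 7.7%.

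A milder case: true rate 20% in both arms, 13.3% leaving one arm, events preceding withdrawal. If patients with an event are twice as likely to leave, the chances of leaving are 0.111 without an event and 0.222 with one (0.8 × 0.111 + 0.2 × 0.222 = 0.133). The expected reported rate is 0.2 × 0.778/0.867, about 18%. If they are three times as likely, it is 16.5%. In 200,000 simulated trials (two-proportion z-test at 0.05), type I error was 6.0% and 8.2%, against 5.0% to 5.1% with the data kept.

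**Power (effect size 0.6, α = 0.00625).**

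| Arms | Two-sided | One-sided |
|---|---|---|
| 75 v 75 | 81.4% | 87.2% |
| 73 v 75 | 80.7% | 86.7% |
| 70 v 75 | 79.6% | 85.8% |
| 65 v 75 | 77.6% | 84.2% |
| 65 v 65 | 73.8% | 81.1% |

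**The case against.** The best case for leaving the rule alone has five parts.

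- **Differential withdrawal is conjecture.** Much of the difference in burden falls before surgery. The later burden (pain logs, therapy measurements, 6-week tests) is the same in both arms. With similar withdrawal the error stays at 5.4% to 5.8%, and the 11% figure needs 10 leavers against none. This stands as a limit on size. It does not justify deleting the data that would show which case occurred.
- **Deletion may not be irreversible.** Blood pressure, laboratory values and knee scores are routine care and may survive in hospital records, and withdrawal counts by arm could still be reported. Partly right, but the rule also bars the data from analysis, so surviving records do not help the trial comparison.
- **Sections 2 and 5 do not strictly conflict.** Events may be reported or reviewed before deletion, and the monitoring plan is only summarised. Correct: the gap is that retention is not stated. The events still leave the final comparison.
- **Power is already protected.** Enrolment was raised to 75, and one-sided power at 65 per group is 81.1%. The 73.8% two-sided figure comes from sidedness: it is what 65 per group gives with no deletion at all. This stands, and the case does not rest on power. Extra enrolment does not correct selection.
- **Time since last drink is a weak example.** The two regimens largely set it, so a false-positive rate means little there. Accepted. The other early outcomes carry the point.

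**Conclusion.** The plan is wrong as written and must be changed. This is an explicit instruction, not missing detail: followed literally, it removes randomised and treated patients because of a post-randomisation event and takes completed outcomes, baseline values and adverse events with them.

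The size cannot be determined from the documents. Under the assumed scenarios it runs from negligible (2 leavers, or the same pattern in both arms) to roughly a doubling of type I error (10 leavers from one arm, r = 0.5). Adverse-event rates can be distorted in either direction. The conclusion does not depend on these figures. It rests on the stated rule and on the fact that, once the data are deleted and barred from analysis, the trial cannot examine or correct the selection.

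**What to change.** Replace the deletion sentence in Patient Withdrawal with wording such as:

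> Data collected up to withdrawal are retained and analysed in the arm to which the patient was randomised; no further study data are collected. Adverse events recorded before withdrawal are kept in the safety data. Other data are removed only if the patient expressly revokes permission to use them. Withdrawals and removals are reported by arm with reasons.

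Then:

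- In section 9, make all randomised patients with available data, analysed as randomised, the primary analysis set, and compare baseline values of leavers and stayers.
- In section 5, state that the quarterly review includes withdrawn patients' events, so that it agrees with the withdrawal paragraph.

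This does not remove selection bias for outcomes due after withdrawal. For those, the retained baseline and early data allow it to be examined.

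The cost is one IRB amendment covering these changes. Consent wording or re-consent is also needed if the consent form repeats the deletion rule; those pages are not in the text available. No extra visits or tests are required.

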***Traditional Intravenous Fluid versus Oral Fluid Administration in Primary
Total Knee Arthroplasty: A Randomized Trial***

Version 8.0 July 6th, 2017 - NCT03719378

Traditional Intravenous Fluid versus Oral Fluid Administration in Primary Total Knee Arthroplasty: A Randomized Trial

1. Purpose: Evidence-based guidelines on optimal perioperative fluid management have not been established in patients undergoing orthopaedic surgery. Typical intraoperative and post-operative fluid management has been arbitrary without evidence based guidelines established following total joint replacement. We have observed many patients post-operatively with side effects such as fluid overload leading to medical complications requiring either prolonged hospitalization or readmission. Additionally, this overload may lead to wound healing complications secondary to fluid shifts which may be devastating in this patient population. Recent randomized trials in major abdominal surgery suggest that large amounts of IV fluid may increase morbidity and hospital stay. Additionally, this increase fluid may be detrimental in patients with anastomosis leading to failure and/or complications in this patient population. We have defined to specific groups of interest to study in this patient population with regards to fluid management. The first group is the “traditional” IV fluid group where the anesthesiologist gives an unspecific amount of fluid intraoperatively and post-operatively the patient gets a set amount of fluid based on “protocol” on the orthopaedic floor (i.e. 75 cc/hour until good oral intake). This is the protocol utilized by most orthopaedic practices throughout the United States. The second group is defined as patients who are given a specific protocol preoperatively to optimize hydration, followed by limited fluids intraoperatively based on physiologic parameters. This study will investigate the effects of two regimens of intraoperative fluid management (“traditional” vs. “oral”) with physiologic and patient function as primary outcome measures after surgery.

2. Procedures:

- Patients meeting the inclusion criteria who are schedule for unilateral primary TKA will be identified.
- The patients will be approached regarding the study (in clinic by research staff) and if the patient is agreeable, informed consent will be obtained.

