There are risks and complications that are associated with all artificial knee surgeries. These have all been discussed with you by your surgeon's team prior to surgery. You are at no increased risk of known complications in this study.

Testing Session Risks:

Though the procedures that you will be exposed to are safe, discomforts you may experience while in this study include:

- Commonly - muscle soreness after muscle strength testing for approximately 2 days after testing. This soreness is similar to the muscle soreness that you may feel if you lift weights or vigorously exercise after a long time off
- Less commonly – muscle strains or tears

The study may also include risks that are unknown at this time.

The investigators have a data safety monitoring plan (DSMP) that includes the Principal Investigator monitoring confidentiality, protection of subject privacy, database protection, confidentiality during adverse event reporting, adverse event information including definitions of adverse events, classification of adverse event severity, adverse event attribution scale, expected risks, adverse event reporting and follow-up, serious adverse event reporting, data quality and management, participant accrual and compliance, measurement and reporting of participant adherence to protocol, designation of an independent physician, informed consent process, and reporting change in study status. In addition, to monitor the safety of the subjects enrolled every quarter an independent physician will review the studies adverse events as well as inclusion/exclusion to ensure there is no increased risk to subjects who are taking part in the study. Study staff will ensure that the IRB is informed in a timely manner of any recommendations, decisions, findings, actions, or steps mandated by the DSMP.

6. Benefits to subjects and/or society.

- Other studies (non-orthopaedic) have shown benefits with wound healing and a potential decrease in adverse events after abdominal surgical procedures. It is unknown if there will be a difference between the two protocols in our study. The potential benefits to the oral group include decreased wound complications, improved functional outcomes and the potential for a decrease in healthcare expenditure per surgery.

Patient Selection Criteria

INCLUSION

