- Patients between the ages of 18-75 years old undergoing a primary total knee arthroplasty for a diagnosis of degenerative osteoarthritis who do not meet the exclusion criteria listed below.

EXCLUSION – patients will be screened for the following exclusion criteria at their routine preoperative appointment with the orthopaedic and internal medicine teams.

- Volume-dependent cardiac conditions:
- Aortic stenosis
- Pulmonary valve stenosis
- Subaortic stenosis
- Severe Aortic Insufficiency
- Chronic systolic heart failure
- Eisenmeinger Syndrome
- Severe pulmonary HTN
- Chronic or paroxysmal dysrhythmias
- Pre-operative electrolyte abnormalities
- Abnormalities of the HPA (hypothalamic-pituitary axis)
- Stage 3 Chronic Kidney Disease (or worse)
- Patients taking angiotensin receptor blockers (ARB)
- Patients with uncontrolled diabetes mellitus (patient with A1C of 7+ or on insulin)
- Patients whose BMI is > 38 or < 19

- Current use of long acting narcotic medication or 3 or more months of daily short acting narcotic medication
- Patients at risk for electrolyte abnormalities, dehydration or intra-operative hypotension. (patients taking angiotensin receptor blockers, ACE inhibitors (48 hours prior to surgery) and Diuretics)
- Patients with severe, untreated or uncontrolled GERD.
- Patients that cannot receive spinal anesthesia (e.g. patient with back fusions)
- Pre-Operative Anemia (pre op HCT <30%)

7. Treatment/Intervention Schedules or in the case of observational studies:

- As per section #2

8. Data Collection Procedures

- Preoperative history and physical will be performed as usual by the surgeon and/or their physician assistant. The patient will also be evaluated preoperatively (per standard procedure) by the general medicine team as well.
- Please refer to section 2 and 8 for the outcome measures, how they will be collected and the time intervals designated.
- Data will be stored on a password protected Microsoft Excel spreadsheet on a Centura approved secure computer.
- All data collected will be de-identified.

9. Methods of Evaluation

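### Section 5 gives an unqualified assurance of no increased risk and names no risk of either fluid regimen; the protocol's own text does not support this, and the quarterly safety review is not asked to compare the arms

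*Combined protocol and SAP*

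**What the plan says.** Section 5 (Description of risks), under its Surgical Risks sub-heading, refers to the complications of knee replacement in general and then says "You are at no increased risk of known complications in this study". Under Testing Session Risks it lists "Commonly - muscle soreness after muscle strength testing for approximately 2 days after testing" and "Less commonly – muscle strains or tears", and closes with "The study may also include risks that are unknown at this time". It says that both groups have the usual postoperative laboratory tests, monitoring and follow-up. It then summarises a data safety monitoring plan (DSMP) whose elements include expected risks and an attribution scale. Under that plan an independent physician reviews adverse events and eligibility every quarter "to ensure there is no increased risk to subjects who are taking part in the study".

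Other parts of the protocol bear on the same point:

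- Section 1 (Purpose) reports that the investigators have seen many patients with "side effects such as fluid overload leading to medical complications requiring either prolonged hospitalization or readmission". It adds that overload may harm wound healing, and that trials in abdominal surgery suggest large IV volumes may raise morbidity and length of stay.
- Section 2 fixes 4 litres of crystalloid within 24 hours in the Traditional arm and caps IV fluid at 500 ml in the Oral arm.
- Section 2, Primary Outcomes, item K records "episodes such as symptomatic hypotension (light-headedness, syncope), emesis, the need the IV fluid boluses". Item O records pressor drugs in both groups.
- Patient Selection Criteria excludes "Patients at risk for electrolyte abnormalities, dehydration or intra-operative hypotension", together with a list of volume-dependent cardiac conditions.
- Section 6 says that a difference between the two protocols is unknown, and lists fewer wound complications among the potential benefits of the Oral arm.

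**The concern.** Section 10 says that the amount of fluid is the only thing that differs between the groups. A reader therefore expects the risk section to deal first with the risks of receiving a fixed large IV volume or a restricted one. It deals with neither. It offers a flat assurance instead, and its only specific study risks come from an outcome measurement.

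Two things are at stake. First, the protocol's statement of risk does not match the rationale on which the trial is built. Second, the safety review inherits the gap. A reviewer asked to confirm that there is no increased risk needs to know increased relative to what, and needs data arranged so that the comparison can be made. The text supplies neither.

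**Working it through.** The plan gives no figure for risk, so there is none to reproduce. The check sets the passages side by side, with simple arithmetic on the fluid volumes.

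**1. Specific study risks in Section 5.** From strength testing: 2 (soreness; strains or tears). From either fluid regimen: 0. General surgical risks and unknown risks are mentioned without detail.

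**2. Size of the randomised contrast.** Inputs are from the two fluid protocols in Section 2.

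- Traditional arm: 2,000 ml (intraoperative) + 500 ml (PACU) + 1,500 ml (inpatient room) = 4,000 ml.
- Oral arm: at most 500 ml IV.
- Ratio: 4,000 / 500 = 8, so at least 8-fold in planned IV volume.
- Planned enrolment: 2 × 75 = 150 patients.

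**3. Is the assurance supported under any comparator?** The word increased needs one, and Section 5 gives none. There are two candidates.

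*One arm against the other.* Section 6 says that a difference is unknown, and names fewer wound complications as a possible benefit of the Oral arm. If one arm may have fewer, the other may have more by comparison. An unknown difference cannot support a statement that risk is not increased.

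*Each arm against usual care outside the trial.* Section 1 describes usual care as an unspecified intraoperative volume, then floor fluid at, for example, 75 ml per hour until oral intake is good.

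- Traditional arm: Section 2 fixes the intraoperative volume and gives 1,500 ml in the inpatient room with no oral-intake endpoint. At 75 ml per hour, 1,500 / 75 = 20 hours. The documents do not say how long usual floor fluid runs. If it ran 8 to 24 hours (an assumed range), the volume would be 75 × 8 = 600 ml to 75 × 24 = 1,800 ml. The fixed volume could thus lie above or below usual care, and the documents do not show that they are equal.
- Oral arm: a 500 ml IV cap departs from what Section 1 says most practices do, so usual care cannot underwrite the assurance here.

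The assurance is therefore not established under either comparator.

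**4. Are the harms known complications on the protocol's own account?** For overload, prolonged stay or readmission, yes: Section 1 reports them as observed. Wound-healing problems are given there as something overload may cause. Hypotension, syncope, emesis, boluses, pressor use and dehydration appear as events to record or as grounds for exclusion. The protocol foresees them but assigns them to neither arm.

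**5. Can the quarterly review answer its own question?** The DSMP summary gives its purpose, but neither a comparator nor a layout by arm. It also does not say that events are pooled or that the reviewer is blinded. The finding is silence on the point. The document describes no blinding that a table by arm would break.

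**The case against.** The best reply is contextual. The sentence stands under Surgical Risks, directly after the general complications of knee replacement, and it speaks of increased risk. Section 1 presents traditional fluids as common practice, so overload can be read as background to usual care. Section 5 also mentions unknown risks and monitoring in both arms, and Section 2 adds blood pressure every 8 hours in hospital and pressor totals. On this view the text is loosely worded, and the relevant harms are being watched.

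Part of this stands. The conflict is less than a strict contradiction, and the monitoring is real. But the usual-care reading does not rescue the sentence: the Traditional arm's volumes are fixed where Section 1 leaves them open, and the Oral arm departs from usual care by design. Recording an event is also not the same as stating it as a risk.

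A reader might go further than the documents allow in four ways:

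- *That the protocol names hypotension as a risk of the restricted arm, or excludes susceptible patients because of the 500 ml cap.* Item K attributes nothing to an arm. The exclusion applies to everyone, and its parenthesis points to ARBs, ACE inhibitors and diuretics. Both arms also receive spinal anaesthesia.
- *That patients were not told of fluid risks.* Consent pages are not in the available text, so nothing follows about them.
- *That the IRB was not told.* An IRB reading this protocol sees Section 1, item K and the exclusions.
- *That the review pools the arms, or that the DSMP's expected risks omit fluid harms.* The text is silent on layout and only summarises the DSMP. There is no event rate from which to calculate what a review might miss.

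**Conclusion.** The point holds as a fault in the risk section and a gap in the description of the safety review. Section 5's assurance is unsupported by Sections 1, 2 and 6 and by the exclusions, and the section names none of the foreseeable risks of the randomised regimens. The review's stated purpose implies a comparison that the text does not ask for.

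In size, it concerns the risk statement for both arms, with planned enrolment of 150 and at least an 8-fold contrast in planned IV volume. It alters no endpoint, estimate or power calculation, and its effect on the detection of harm cannot be quantified from the documents. It should be corrected because it bears on safety oversight and is cheap to correct.

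The conclusion assumes that the DSMP is no more specific than its summary in Section 5. If the full plan already lists fluid-related risks and tabulates events by arm, only the wording of Section 5 remains to be reconciled.

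**What to change.** 1. Delete the no-increased-risk sentence, or qualify it so that it names its comparator and agrees with Section 6 that a difference is unknown.
2. Reconcile Section 5 with Sections 1, 2 and 6 and the exclusion criteria. State the overload and wound-healing risks that Section 1 already names. State hypotension, syncope, emesis, need for boluses or pressors, and dehydration as possible risks under study, not attributed to an arm.
3. Carry the same list into the DSMP's expected risks, and check any consent wording against it.
4. Say that the independent physician receives adverse event counts by arm each quarter, with the number of patients in each arm as denominator, and that the comparison between arms is the basis for judging increased risk.

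The cost is a wording amendment through the IRB and one two-column table per quarter for a reviewer who is already in place. No fluid volume, eligibility rule or other clinical rule needs to change for this.
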